8.2.4 Comparator(s)

The intervention will be compared against a waitlist group. This comparator was selected to compare Wysa to the current standard of care for patients waiting for standard IAPT assessment and treatment.

8.2.5 Outcomes

8.2.5.1 Primary Outcomes

The primary analysis will be the comparison of depression severity between users of the app and patients in the standard clinical pathway (see Table 5). The primary outcome will be measured at baseline and three months post randomisation. In line with the national recommendations laid out by the IAPT Manual, we will be using Wysa's AI automation to encourage users to complete the Patient Health Questionnaire (PHQ-9 [36]) and General Anxiety Disorder (GAD-7 [37]) routine outcome measures [2]. Depression severity was chosen as the primary outcome because the PHQ-9, a depression symptom measure, is recommended for use in all patients presenting to IAPT services [2].

Table 5. Primary Outcome Measurement

Primary Outcome	Outcome Measure
Depression severity	
Score on the PHQ-9 [36]

8.2.5.2 Secondary Outcomes

There will be several secondary outcome measures to assess Wysa's ability to improve anxiety severity and identify people who need urgent support, engagement, and the acceptability and cost-effectiveness of the app (see Table 6). The secondary outcomes will also be measured at baseline and 3 months post randomisation.

Anxiety severity

As the GAD-7 [37], which measures anxiety symptoms, is recommended for the 6 most common presentations, it will also be used as an outcome measure for the study and will be presented to patients through the app in the same way as the PHQ-9 [36]. The remaining measures used by IAPT

are linked to specialist presentations of pre-existing conditions which would be excluded as participants from the study due to non-eligibility to IAPT standard pathway.

Crisis identification

Wysa's ability to identify users who are at high risk of a crisis and who need to be provided with additional support will be measured by comparing the number of patients that Wysa flags for escalation with the number of patients in the control group who contact the NHS Trust's crisis helpline or attend A&E. This data will be collected from iaptus, a cloud-based electronic patient record for managing psychological therapy services [38], which flags patients on the waitlist who access these crisis services.

Engagement

User engagement with Wysa will be assessed using a combination of complementary measures. Examining time spent using a digital health intervention is not by itself a reliable measure of effective engagement, as it cannot differentiate between users who spend a long time on the app because they're positively engaged compared to those who are frustrated and struggling to use it [39]. Therefore, objective measures of app usage will be supplemented with an assessment of uptake and dropout rates and a qualitative exploration of subjective user experience and engagement behaviour.

Acceptability

Wysa's acceptability will be examined through qualitative semi-structured interviews in a subset of participants. These interviews will provide a means of collecting in-depth data about participants' experiences with Wysa, what they liked and disliked, and why.

Health-related quality of life

Two questionnaires will be used to assess health-related quality of life: the EQ-5D-5L [40] and the Short Form 12 (SF-12) health survey [41]. The EQ-5D-5L provides a descriptive self-assessment of health in 5 dimensions: mobility, self-care, usual activities, pain/discomfort and anxiety/depression [40]. It is commonly used as a quality of life measure to conduct cost effectiveness analyses [42]. The EQ-5D-5L has a greater emphasis on physical than mental health, but has demonstrated the ability to capture changing anxiety severity [43]. The SF-12 survey is a reliable measure of functional health and is well-suited for this study, as it includes mental health items and has been shown to be acceptable for use as a screening tool for depressive disorders [44].

Cost-effectiveness

To conduct a health economic analysis, the study will collect data on health and social care service use, medication use and treatment costs, the implementation costs of Wysa, out of pocket medical expenses borne by patient and carers and productivity related costs such as work absence / time off work due illness. This data will be combined with the quality-of-life indicators to produce an assessment of the costs of adopting Wysa from the perspective of both the UK health and social care services and the wider society [45]. This analysis will also produce a budget impact model for each site that will be used to provide a final overall implementation strategy for more rapid adoption at other NHS sites and dissemination across the AHSN network in partnership with the new Integrated Care Systems. The team will also incorporate the environmental sustainability calculation in line with the Greener NHS agenda.

Table 6. Secondary Outcome Measurement

Secondary Outcome	Outcome Measure
Anxiety severity	
 Score on the GAD-7 [37]
Crisis identification	
 Number of users identified by the app for escalation of care compared to the number of patients in the control group who access A&E or out-of-hours services while waiting for treatment
Engagement	
 Uptake rates Dropout / 'did not attend' rates App usage data Qualitative feedback from semi-structured interviews
Acceptability	
 Qualitative feedback from semi-structured interviews Automated review questions periodically requested during general use of the tool
Health-related quality of life	
 EQ-5D-5L [40] Short Form 12 (SF-12) health survey [41]
Cost-analysis	
 Data on health and social care service use, medication use and treatment costs, patient-bourne costs, productivity related costs, and Wysa's implementation costs

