6 STUDY FLOW CHART

This project will conduct a real-world evaluation of Wysa as an early intervention tool introduced into the mental health referral pathway for adult IAPT service. There is currently an average wait time for IAPT between referral and treatment start of 8+ weeks with 95% of people starting treatment within 18 weeks [1]. Wysa will be made available to patients upon referral to IAPT. The control group will continue with service as usual whilst the test group will interact with Wysa while waiting for treatment.

Wysa will remain available to patients throughout their progression through the standard clinical pathway. Patients will be provided with information about the study at their initial referral point and will be contacted by our research assistants to collect informed consent and provide the product link. This will enable Wysa to offer immediate support tools and monitoring. While patients are waiting for treatment, Wysa will serve as a screening support tool for flagging assessment needs to the clinical team. After patients have received treatment, Wysa can be used as an extended monitoring tool. This is in line with the IAPT manual 2018's future goal [2] of using an app to prompt patients to fill in key outcome measures at regular intervals during the follow-up year, providing patients with easy access to their relapse prevention plan, alerting the service if relapse has occurred, and facilitating the scheduling of booster sessions. Figure 1 demonstrates the current clinical IAPT pathway with the proposed study procedures in blue.

[figure not shown]

Figure 1. Current clinical pathway for adult IAPT referral and proposed study procedures (blue) (adapted from [2])

Based on the artificial intelligence (AI) recommendations generated by Wysa, patients may be passed to the IAPT for a full assessment using a combination of outcome measure scores and language used within the tool. A copy of the patients' responses to outcome measures will be

automatically pushed into their electronic patient record through the Mayden clinical information system and an automated email will be sent to the referrals coordinator to flag the need for onward referral.

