Wysa will have two pathways to crisis alert and response. The first pathway is for patients to trigger the crisis response pathway by pressing a manual override button on the app. The second pathway is for the app to trigger the crisis response because of an individual's response to an outcome measure or the language used in free conversation with the AI. Because this pathway can be triggered by the app's natural language processing, the AI regularly checks in with the patient to ensure they are understanding them correctly.

When Wysa or the user triggers the crisis response pathway, users will be provided with a stepped crisis plan including grounding exercises, local crisis helplines, or a recommendation to attend A&E where there is significant injury or risk to life. Data will be collected indicating the number of false positives identified by the AI. Coinciding with this, the app pushes an update to the patient's linked electronic patient record through Mayden and sends an alert email to the 'Clinician of the Day' at each trust for human follow up.

[figure not shown]

Figure 2. High-level study Gantt chart

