7.5 Aims and Objectives

The primary aim of this project is to establish real-world efficacy that patient use of Wysa while waiting for treatment through the NHS mental health care pathway positively impacts well-being by comparing system users with standard services users.

The secondary aims of this project are:

1. To examine the feasibility of using Wysa to identify users at high risk of a mental health crisis and escalate them to further care;
2. To examine levels of user engagement with Wysa;
3. To evaluate patient acceptability of an autonomous early intervention supporting mental health services;
4. To complete a full health economic assessment of using Wysa for autonomous early intervention and triaging support;
5. To assess the potential for sustainable adoption of Wysa in mental healthcare pathways.

[figure not shown]

Figure 3. Wisconsin logic diagram

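### The crisis-identification outcome sets app flags in one arm against crisis-service use by different patients in the other, so it cannot measure how well the app identifies users at high risk

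*Protocol*

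**What the plan says.** - **Protocol 8.2.5.2, Crisis identification.** The app's ability to pick out users at high risk is to be assessed through "comparing the number of patients that Wysa flags for escalation with the number of patients in the control group who contact the NHS". The sentence goes on to define the control event as contact with the Trust's "crisis helpline or attend A&E". The source is the iaptus record, "which flags patients on the waitlist who access these crisis services".
- **Protocol Table 6.** Same structure, different control event: "Number of users identified by the app for escalation of care compared to the number of patients in the control group who access A&E". To A&E the table then adds a second kind of contact and a window: "or out-of-hours services while waiting for treatment". The opening of 8.2.5.2 places the secondary outcomes at baseline and three months after randomisation.
- **Protocol 7.5, secondary aim 1.** "To examine the feasibility of using Wysa to identify users at high risk of a mental health crisis and escalate them to further care".
- **Protocol section 6.** Two app outputs could count as a flag. For a full assessment, "an automated email will be sent to the referrals coordinator to flag the need for onward referral". For a crisis, the user can press a button, or the app acts: "The second pathway is for the app to trigger the crisis response". The section also says that AI false positives will be counted, but not against what standard.
- **Allocation.** Protocol 8.3.2.1 has 2:1 in favour of usual care. The SAP (Randomisation – implementation) has 2:1 in favour of the intervention.
- **SAP, Statistical methods.** Comparative analysis is described for PHQ-9 and GAD-7 only.

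**The concern.** A claim that a tool identifies people at risk needs two facts about the same person: whether they were flagged, and whether they had the event or need. The planned outcome takes the first from the intervention arm and the second from the control arm. One is an output of the app; the other is help-seeking by patients who did not have the app. Crisis contacts by unflagged intervention patients, which would be the missed cases, do not enter the outcome.

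The risk lies in interpretation. Similar figures in the two arms could be quoted as evidence that the app finds the right patients, although they fit almost any level of accuracy. Protocol 10.1 intends the results to support Class IIa regulatory approval and wider adoption, so the wording matters.

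**Working it through.** **Inputs.** 480 randomised (Protocol 8.3.2.1), so arms of 320 and 160 whichever way the ratio runs; attrition is ignored. Crisis rates are assumptions. The 11% (A&E) and 38% (crisis services) are background figures in Protocol 7.1. They are probably too high here, because 8.3.1.2 excludes suicidal ideation and PHQ-9 above 15, so 5% is added as a lower value.

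**The plan's own figure.** There is none for this outcome. The only design figure is 393 for PHQ-9. The smaller arm is (1 + 1/2) × (1.96 + 0.84)² × 6.6² / 2², about 128.2, rounded up to 129; with 258 in the other arm this makes 387, close to 393. Nothing below depends on it.

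**Step 1: what the counts can identify.** Among N intervention patients let F be flagged, C have a crisis, and TP be both. Sensitivity = TP/C and PPV = TP/F. If only F and C are known, TP can be anything from max(0, F + C − N) to min(F, C). The outcome supplies F. C has to be borrowed from the control arm, which assumes that the app does not change crisis risk. TP is not part of the outcome.

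**Step 2: flag rate equal to crisis rate, N = 160.**

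| Assumed rate | F = C | TP | Sensitivity | PPV |
|---|---|---|---|---|
| 5% | 8 | 0 to 8 | 0% to 100% | 0% to 100% |
| 11% | 18 (17.6) | 0 to 18 | 0% to 100% | 0% to 100% |
| 38% | 61 (60.8) | 0 to 61 | 0% to 100% | 0% to 100% |

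In the 11% row the report would show 18/160 flagged (11.3%) beside 35/320 controls with an event (10.9%). With N = 320 (F = C = 16, 35 or 122) the ranges are the same.

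**Step 3: equal raw numbers.** The text compares numbers, not proportions, so equal counts mean unequal rates. With C set to the control rate:

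| Ratio and rate | Flags | Control events | Expected C | Consequence |
|---|---|---|---|---|
| Protocol, 11% | 35/160 (21.9%) | 35/320 (10.9%) | 18 | PPV at most 18/35 = 51%; sensitivity 0% to 100% |
| SAP, 11% | 18/320 (5.6%) | 18/160 (11.3%) | 35 | Sensitivity at most 18/35 = 51%; PPV 0% to 100% |
| Protocol, 38% | 122/160 | 122/320 | 61 | TP 23 to 61; sensitivity 38% to 100%; PPV 19% to 50% |

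These limits hold only if crisis risk is unchanged. For example, 60 flags against 18 expected crises caps PPV at 18/60 = 30%. If the app halved or doubled crises (9 or 36), the cap would be 15% or 60%.

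**Step 4: definitions side by side.**

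| Component | One place | Another place |
|---|---|---|
| Control event | Crisis helpline or A&E (8.2.5.2 text) | A&E or out-of-hours services (Table 6) |
| Window | Three months after randomisation (8.2.5.2 text) | The wait for treatment (Table 6) |
| Flag | Onward-referral email (section 6) | Crisis alert, triggered by app or user (section 6) |

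**Step 5: precision of a within-arm analysis.** Exact (Clopper-Pearson) 95% CIs with sensitivity near 50%:

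| Assumed rate | 160 intervention patients | 320 intervention patients |
|---|---|---|
| 5% | 4/8: 16% to 84% | 8/16: 25% to 75% |
| 11% | 9/18: 26% to 74% | 18/35: 34% to 69% |
| 38% | 30/61: 36% to 62% | 61/122: 41% to 59% |

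The half-width for a between-arm risk difference, 1.96 × √[p(1 − p)(1/320 + 1/160)], is 4.1, 5.9 and 9.2 percentage points at 5%, 11% and 38%.

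**The case against.** **The aim is feasibility.** No section promises sensitivity or PPV, and flag counts do describe feasibility. The construct is being at high risk and needing support, so a flagged user whose crisis is averted is a success, not a false alarm. This stands, and it limits the size of the point. It does not rescue the wording of 8.2.5.2, which presents the cross-arm comparison as the measure of ability to identify.

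**Other parts of the plan might fill the gap.** The false-positive count in section 6 could inform PPV. But it has no stated reference standard, lies outside this outcome and says nothing about missed crises. Protocol 8.5.1 plans intention-to-treat regression for secondary outcomes with 95% CIs, and 8.5.2 puts the interval before the p-value. Regressing on arm would still compare a flag with a service contact.

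**Stronger readings that the documents do not support.**
- A reader might infer that missed crises will go unrecorded. Intervention patients are on the waitlist too, iaptus flags waitlist patients who use crisis services, and service-use data are planned for the economic analysis. The events are probably recorded; this outcome does not use them.
- A reader might infer that similar counts always leave accuracy wholly open. That holds for similar rates. Equal raw counts across 2:1 arms do limit one or both measures, if crisis risk is unchanged (Step 3).
- A reader might infer that no time window is given. Two are given, and they differ.

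**Conclusion.** The point holds. As written, the outcome cannot show that the app identifies users at high risk, because flags and crises are never cross-classified in the same people. At matching rates, sensitivity and PPV are unrestricted, and this does not depend on which of the three assumed crisis rates is used. The limits in Step 3 do depend on the assumed rate and on unchanged crisis risk. The use of raw numbers, the opposite 2:1 directions, the two event definitions, the two windows and the undefined flag make the result harder still to read.

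The reach is narrow: one secondary outcome with a feasibility aim. The primary PHQ-9 analysis is untouched. Nothing here shows that the app detects poorly; the planned comparison cannot tell either way. The change is worth making.

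**What to change.** 1. Keep reporting the planned comparison, as it was prespecified, but as proportions of those randomised and with a statement that it does not measure identification or accuracy.
2. Within the intervention arm, report the proportion flagged. Cross-tabulate app-triggered flags against iaptus-recorded crisis contacts, including contacts by unflagged patients. Give sensitivity and PPV with exact 95% CIs, and show user-triggered alerts separately.
3. Report the same crisis-service event in each randomised arm as a descriptive risk difference with a 95% CI.
4. Reconcile the 8.2.5.2 text and Table 6 to one event definition and one window, state which flag is meant, and reconcile the allocation direction between protocol and SAP.
5. Label the added analyses post hoc if they are specified after the data were seen; the SAP is largely in the past tense.

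**Cost.** Revised wording, written definitions and one iaptus extract run for both arms; the planned service-use data may cover part of item 3. Coverage of iaptus after patients leave the waitlist, and for out-of-hours contacts, must be checked first.

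**Limits to state.** Estimates will be imprecise (Step 5). Under section 6 a flag can prompt crisis contact, through helpline details or advice to attend A&E, or avert it, through grounding exercises and clinician follow-up. The accuracy figures may therefore be biased in either direction and should stay descriptive.

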8.3.2 Sampling

8.3.2.1 Sample Size

Approx 1100 eligible patients are seen per month at the IAPT in the CNWL NHS Foundation Trust. Preliminary work suggests that Wysa is associated with a mean clinical improvement in PHQ-9 of 5.84 (SD6.66) [28]. This study is powered to detect a clinically meaningful effect on the PHQ-9 scale [28]. Based on a SD of 6.6 and a 2:1 recruitment ratio (usual care: intervention) a sample size of 393 would allow detection of a difference in PHQ-9 of at least 2 points, with 80% power. Augmenting the sample size to 480 would allow for 20% attrition, whilst still maintaining sufficient power to detect clinically and statistically meaningful differences with a Type 1 error rate of 0.05. This inflated sample size would also allow for adjustment for stratification variables, gender, age, ethnicity, self-reported antidepressant use, and severity of depression.

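### The crisis outcome compares patient counts with no denominator between 2:1 arms, gives two lists of control events, and states a counting window for controls only

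*Protocol*

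**What the plan says.** The crisis outcome is defined twice in Protocol 8.2.5.2. The text under Crisis identification describes "comparing the number of patients that Wysa flags for escalation with the number of patients in the control group", and the control patients it counts are those that "contact the NHS Trust's crisis helpline or attend A&E". Table 6 gives "Number of users identified by the app for escalation of care compared to the number of patients in the control group", and it restricts the controls counted to those "who access A&E or out-of-hours services while waiting for treatment". Neither place mentions a proportion, a rate or the number randomised.

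The text takes the control events from iaptus, "which flags patients on the waitlist who access these crisis services". The opening of 8.2.5.2 sets the secondary outcomes at baseline and 3 months. Section 6 says that "Wysa will remain available to patients throughout their progression through the standard clinical pathway".

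On arm sizes, Protocol 8.3.2.1 uses a "2:1 recruitment ratio (usual care: intervention" split, so usual care is the larger arm. The SAP, under Randomisation – implementation, has the 2:1 ratio favouring the intervention.

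On analysis, Protocol 8.5.1 says in general terms that comparisons for primary and secondary outcomes will be by intention to treat with linear or logistic regression. It does not name the crisis outcome. The SAP's statistical methods cover PHQ-9 and GAD-7 only.

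**The concern.** A comparison of counts can be read only if both counts have the same chance of arising when nothing differs between the arms. Here three things get in the way.

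- **Denominator.** The arms differ two-fold in size, so equal risks give unequal counts.
- **Event list.** The text counts the Trust helpline and A&E; Table 6 counts A&E and out-of-hours services. A control patient who contacts only the helpline is plainly an event under the text but is not named in the table. A patient who uses only some other out-of-hours service is the reverse.
- **Window.** Control events are tied to the wait. Nothing says when counting of app flags stops.

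This is the only comparative measure the protocol gives for its first secondary aim (7.5), which concerns identifying and escalating users at high risk. Section 10.1 says the trial's data will support a regulatory submission and wider adoption, so a crisis result driven by arm size or waiting time could mislead in either direction.

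**Working it through.** **1. The plan's own figure.** The documents give no event rate or power for the crisis outcome. The only stated size is for PHQ-9 (Protocol 8.3.2.1): 393, raised to 480. For a two-sided 5% test, 80% power, a 2-point difference and 2:1 arms, the smaller arm needs (1 + 1/2) × (1.960 + 0.842)² × SD² / 2².

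- SD 6.6: 128.2, rounded up to 129; total 3 × 129 = 387.
- SD 6.66 (the preliminary-work value in the same section): 130.6, rounded up to 131; total 3 × 131 = 393, as stated.

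I take the planned 480 as given. A 2:1 split makes arms of 320 and 160.

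**2. Equal risk, raw counts.** Expected count = arm size × risk. The 5% is illustrative and does not come from the documents.

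| Ratio used | Intervention | Control | Count ratio |
|---|---|---|---|
| Protocol 8.3.2.1 (160 : 320) | 160 × 0.05 = 8 | 320 × 0.05 = 16 | 0.5 |
| SAP (320 : 160) | 320 × 0.05 = 16 | 160 × 0.05 = 8 | 2.0 |

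The risk cancels from the ratio, so the two-fold gap holds at any common risk. Its direction depends on which document's ratio was used. Dividing each count by the number randomised gives 5% against 5%, a ratio of 1.0, under either allocation.

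**3. The two event lists side by side.**

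| Contact | Text of 8.2.5.2 | Table 6 |
|---|---|---|
| A&E | counted | counted |
| Trust crisis helpline | counted | not named |
| Other out-of-hours service | not named | counted |

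No other section settles which list applies.

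**4. The window, after denominators are put right.** Inputs: a wait averaging 8 weeks or more from referral to treatment start (Protocol section 6), and 3 months taken as 13 weeks. Assumptions: a constant event rate λ, everyone observed, one wait length for all participants, and flags counted for the full 13 weeks.

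- λ = −ln(1 − risk over 13 weeks) / 13.
- Control proportion over a wait of w weeks = 1 − exp(−λ × min(w, 13)).

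| Wait | 13-week risk 5%: control proportion (ratio) | 13-week risk 11%: control proportion (ratio) |
|---|---|---|
| 8 weeks | 3.1% (1.61) | 6.9% (1.59) |
| 12 weeks | 4.6% (1.08) | 10.2% (1.08) |
| 13 weeks or more | 5.0% (1.00) | 11.0% (1.00) |

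The spurious ratio therefore runs from about 1.6 down to 1.0. The quoted wait starts at referral, whereas the counting here starts at randomisation. A shorter remaining wait would raise the ratio, but the documents do not say how much shorter it is.

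**The case against.** The strongest reply on arm size is Protocol 8.5.1. Whether a patient had an event is naturally a yes/no item, and a logistic regression by randomised arm uses the arm denominators, so the two-fold gap would vanish. That is correct if the rule is applied per patient. But 8.5.1 does not assign a model to this outcome, 8.2.5.2 asks for counts in both places, and the SAP leaves the outcome out. Regression would also leave the two event lists and the window untouched.

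On the window, a reader might infer that app flags certainly run beyond the wait, because Wysa stays available along the pathway. The documents do not establish this. Section 6 also describes Wysa flagging needs while patients wait, and the GP letter in Appendix 4 describes use during the wait. The waiting clause in Table 6 could even be read as covering both sides. What stands is an omission: no window is stated for flags, so the 1.6 is conditional.

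Three other readings go too far. One multiplies the two-fold count gap by the window ratio into a single larger distortion; that stacks an inferred window on an allocation ratio on which the documents disagree. Another sizes the effect of the two lists from the background percentages in 7.1 for crisis services and A&E. Those do not map onto the lists: A&E is in both, and crisis services are not said to mean the Trust helpline. A third says the differing lists make identical arms differ. They leave the control count undefined, which is a different fault.

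It is also fair to say that an app flag and a service contact are different events, so equal risk across them is only a device for testing the counting rule. And comparing service use by arm does not answer whether the app identifies people in need, which is why flags should still be reported in their own right.

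**Conclusion.** The concern holds in limited form. Followed as written, the measure gives a two-fold difference in counts when risk is equal, at any risk level. The direction is set by an allocation ratio on which protocol and SAP contradict each other. The control count is undefined because two event lists are given. The counting window is stated for controls only; the resulting bias lies between none and a ratio of about 1.6 for waits from 13 weeks or more down to 8 weeks. That range rests on a constant rate, 13 weeks of flags and a wait counted from randomisation.

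A reader might conclude that the trial's crisis result will certainly be wrong. The documents do not go that far: a per-patient analysis with an agreed list and window would be sound in these three respects, but the plan does not commit to one. This is a secondary outcome, so the primary PHQ-9 comparison is unaffected. The definition should be corrected before the crisis comparison is reported.

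**What to change.** In Protocol 8.2.5.2, Table 6 and the SAP:

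- Use one event list: Trust crisis helpline, out-of-hours service, A&E.
- Report, by arm, the proportion of randomised participants with at least one such contact, over the same window in both arms.
- Set that window as randomisation to 3 months if iaptus records contacts after treatment starts. Appendix 4 gives controls the app only after 3 months, so they are without it throughout. If iaptus does not record these contacts, use the waiting period in both arms and add a rate per person-week.
- Report app flags separately, as a proportion of the intervention arm over the same window, and not against control service use.
- Reconcile the direction of the 2:1 ratio between Protocol 8.3.2.1 and the SAP.

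The cost is rewording in the protocol, a new entry in the SAP (which has none for this outcome) and possibly a wider iaptus extract. The documents describe only a waitlist flag and do not show that later contacts are held. Contacts after treatment starts may be incompletely recorded, and the report should say so. The SAP is dated 8 August 2023 and is written largely in the past tense, so a redefinition after that date must be labelled post hoc.
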